10.7 PRIMARY EFFECTIVENESS ANALYSIS

10.7.1 Primary Effectiveness Hypothesis

The primary effectiveness research hypothesis is that the treatment success rate at one year exceeds a performance goal of 80%. The null and alternative hypothesis is presented below.

$$H_0: P \leq 0.80 \quad \text{vs.} \quad H_a: P > 0.80$$

Where P is the rate of Treatment Success as defined in §10.7.2.

10.7.2 Sample Size

The primary trial effectiveness variable is the Treatment Success rate at one year post-operatively. Treatment Success is a composite of clinically-relevant outcomes, including procedural technical success and absence of: aneurysm rupture, conversion to open repair, Type I endoleak after 30 days; Type III endoleak; clinically significant migration; aneurysm enlargement; or secondary intervention for resolution of endoleak, limb occlusion, migration, aneurysm sac expansion and/or a device defect.

The sample size is obtained by using the exact binomial distribution using PASS 2008. A sample size of 82 patients at one year in the test group will have 80.58% power against a null performance goal of 80% if the proportion of Treatment Success is 90% or higher for alpha = a one-sided 0.05. It is estimated that the rate of Treatment Success will be greater than 90%.

It is anticipated that the drop-out rate of the trial will be 15% or less. Because the larger of the two sample sizes after adjustment for loss to withdrawal is the one for effectiveness, $82/0.85 = 97$ patients will need to be recruited for this trial.

10.7.3 Analysis Plan

The primary effectiveness analysis will compare the Treatment Success rate as defined previously to a target rate of 80%. The null and alternative hypotheses are defined below.

$$H_0: P_t \leq 0.80$$

$$H_1: P_t > 0.80$$

Where P_t = the proportion of treated patients who meet the Treatment Success definition. The observed proportion of patients with Treatment Success at one year post-procedure will be tested with the exact binomial distribution under the null hypothesis given in the inequality above. The formula for this expression is presented below.

$$P(X > x_t | 0.80) = \sum_{k=x_t}^{n_t} \binom{n_t}{k} 0.80^k 0.20^{n_t-k} < 0.05$$

Where x_t is the number of successes at one year and n_t is the number evaluated. If the one-sided P-value is less than 0.05, the null hypothesis will be rejected and the study hypothesis will be demonstrated.

If the study site success proportions across study site are not homogeneous, then the method of Fleiss described above will be used in the Test arm only to obtain a weighted estimate of the proportion successful. The mean proportion is found the same way as the first equation above. The test statistic becomes a z-statistic with the following formula:

$$z = \frac{(\bar{p}_T - 0.80)}{SE(\bar{p}_T)}$$

Where the formula for the weighted estimate of the proportion is given by the following formula.

$$\bar{p}_T = \frac{\sum_k W_k p_{Tk}}{\sum_k W_k}$$

And the formula for the weight in site k is given by the following

$$W_k = \frac{1}{n_k} p_k (1 - p_k)$$

And the formula for the standard error is given by the following.

$$SE(\bar{p}_T) = \left(\sum_{k=1}^{m_T} W_{Tk} \right)^{-1/2}$$

If the $z < 1.645$ ($P=0.05$, one-sided), then the null hypothesis will be rejected in favor of the alternative and the primary effectiveness endpoint will be achieved.

To determine those factors that may be associated with Treatment Success, covariate analyses will be performed by logistic regression to determine if there are differences in the Treatment Success rates in the Test group when adjusted for other factors. Possible covariates eligible for these analyses will be age, gender, ASA class, cardiac/coronary artery disease (a composite variable to include arrhythmia, CHF, prior MI, CABG/PCI, heart valve repair/replacement), cancer, cerebrovascular disease, COPD, diabetes, hypertension, liver disease, peripheral arterial occlusive disease, renal failure, smoking, maximum aneurysm diameter, and study site. Because there are too many possible covariates to include in a model, screening is necessary to reduce the number of eligible covariates for consideration in the final model. Screening logistic regression models to include only the covariate, will be used. If the P-value for the screening model for the covariate is less than 0.20, the covariate will be included in the competition for the final model. The final model will be obtained by manual backward elimination to have the seven or fewer covariates with P-value less than 0.05.

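### The exact-test formula for primary effectiveness (10.7.3) contradicts itself: its label excludes the observed count while its sum includes it; the sum is right and the label needs one symbol changed.

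*Combined protocol and SAP*

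**What the plan says.** Section 10.7.1 sets the hypothesis: "The primary effectiveness research hypothesis is that the treatment success rate at one year exceeds a performance goal of 80"%. Section 10.7.2 states the method, "The sample size is obtained by using the exact binomial distribution using PASS 2008", and the result: "A sample size of 82 patients at one year in the test group will have 80.58% power" against the 80% goal, "if the proportion of Treatment Success is 90% or higher for alpha = a one-sided 0.05".

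Section 10.7.3 gives the decision rule. The formula reads "P(X > x_t | 0.80) = \sum_{k=x_t}^{n_t", followed by the binomial terms with probabilities 0.80 and 0.20, and the whole is required to be below 0.05. Here x_t is the number of one-year successes and n_t the number evaluated. The text then says: "If the one-sided P-value is less than 0.05, the null hypothesis will be rejected and the study hypothesis will be demonstrated". No pass count is printed anywhere in 10.7.

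**The concern.** For the alternative that the success rate exceeds 80%, the exact one-sided P-value is the probability under 80% of a count at least as large as the one observed, P(X ≥ x_t). The sum from k = x_t is that quantity. The label on its left, P(X > x_t), is the same tail without the observed count. The line equates two quantities that differ by P(X = x_t).

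This line is the decision rule for the primary effectiveness claim. With 71 successes in 82 patients, one side of the equation passes the trial and the other fails it. The label is also an easy side to code by accident, since one minus the binomial distribution function at x_t returns exactly P(X > x_t), and there is no printed cut-off that would expose the slip.

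**Working it through.** **Inputs.** Null rate 0.80 (10.7.1); assumed true rate 0.90, one-sided alpha 0.05, 82 evaluable patients and power 80.58% (10.7.2); rejection when the one-sided P-value is below 0.05 (10.7.3); drop-out at most 15% and 97 recruited (10.7.2).

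**Formulas.**
- Sum form: reject at the smallest r with P(X ≥ r | n, 0.80) < 0.05.
- Label form: reject at the smallest r with P(X > r | n, 0.80) < 0.05, that is, P(X ≥ r + 1 | n, 0.80) < 0.05.
- In both cases the error is P(X ≥ r | n, 0.80) and the power is P(X ≥ r | n, 0.90).

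**Step 1: reproduce the plan's own figures.** At n = 82 under 0.80:
- P(X ≥ 71) = 0.0836
- P(X ≥ 72) = 0.0458
- P(X ≥ 73) = 0.0228

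The sum form therefore rejects at 72. Its power is P(X ≥ 72 | 82, 0.90) = 80.57%, which agrees with the printed 80.58% to within 0.01 percentage points. The recruitment figure also reproduces: 82/0.85 = 96.47, rounded up to 97.

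**Step 2: the label form at the same n.** P(X > 71) equals P(X ≥ 72) = 0.0458, which is below 0.05, so 71 successes would pass. The true error of that rule is P(X ≥ 71) = 8.36%, and its power is 88.47%. That does not match the printed 80.58%.

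**Step 3: the term in dispute.** At 71 of 82 the sum gives 0.0836 (do not reject) and the label gives 0.0458 (reject). The difference, 0.0836 − 0.0458 = 0.0378, is P(X = 71).

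**Step 4: other numbers evaluated** (complete binomial data, no imputation).

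| n | Form | Reject at | One-sided error | Power at 0.90 |
|---|---|---|---|---|
| 82 | sum | 72 | 4.58% | 80.57% |
| 82 | label | 71 | 8.36% | 88.47% |
| 97 | sum | 85 | 3.46% | 83.01% |
| 97 | label | 84 | 6.22% | 89.69% |

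For n from 82 to 97 the label form's error runs from 5.1% (n = 87) to 8.4% (n = 82). It cannot fall below 5% at any n, because its cut-off is one less than the smallest count whose tail is under 0.05. The range shows the size of the excess and is not separate evidence of a fault.

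**Step 5: the companion formula in 10.6.4.** The exact safety test against 56% is labelled inclusively, P(X ≤ x_t), but its sum starts at k = 1. The omitted k = 0 term is 0.44 raised to the power n_t. At n = 97 its base-10 logarithm is 97 × log10(0.44) = 97 × (−0.3565) ≈ −34.6, so the omission has no numerical effect.

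**The case against.** The strongest reply is that the plan already settles which side governs. The sum is the expression that can be computed, and the comparison with 0.05 is attached to it. The text calls the result a P-value, which by definition includes the observed count. The printed power reproduces only with the sum, and the companion safety test in 10.6.4 is labelled inclusively. Section 10.3 also makes SAS defaults the algorithm unless otherwise specified, so the test need not be hand-coded from the label. All of this stands, and it makes the label very probably a slip of notation.

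A reader might infer that the planned test has a one-sided error of 8.4%. The documents do not support that. The error arises only if the label is coded in preference to the sum, and 82 patients is the worst case in the 82 to 97 range. A reader might also infer that the trial's rule is simply 72 of 82, or 85 of 97. That is not supported either. Section 10.1 makes the primary analysis intention-to-treat with imputation. Section 10.2 expects about 15 missing one-year outcomes and combines ten hot-deck imputations by Rubin's method. Section 10.7.3 substitutes a weighted z-test when sites are heterogeneous. The counts describe the simple exact test on complete data.

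It is fair to add that the point turns on one symbol, and an equality bar can be lost in text conversion. This looks unlikely, since the ≤ signs in 10.6.4 and 10.7.3 survive, but the symbol should be checked in the PDF.

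What remains is that a prespecified primary rule should not state a false equality, and a programmer has no printed cut-off to check against.

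**Conclusion.** The formula in 10.7.3 is wrong as written, in its label only. The sum from k = x_t is the correct one-sided P-value and is consistent with 10.7.2. Coding the label literally would move the cut-off by one success, from 72 to 71 of 82, and raise the one-sided error from 4.58% to 8.36%. The sample size of 82 evaluable and 97 recruited, the stated power and the evident intention are unaffected.

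These figures assume complete binomial outcomes and homogeneous sites. They are not the operating characteristics of the multiply imputed primary analysis. The point is a specific correction to a primary decision rule and does not challenge the design.

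**What to change.** In 10.7.3, replace the left-hand side with P(X ≥ x_t | 0.80) and keep the sum from k = x_t to n_t.

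A pass count is optional. If one is quoted, give 72 of 82 as the design cut-off for complete data with homogeneous sites, and say that it is not the decision rule under the multiple-imputation intention-to-treat analysis or the site-heterogeneity z-test.

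In the same edit, start the 10.6.4 sum at k = 0; this is editorial only.

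The cost is one symbol, one optional sentence and one editorial index. No change to sample size, alpha or conduct is needed.

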10.3 GENERAL NOTES

Analyses of MAEs and other adverse events will be conducted at exact time points. Early events are defined as those occurring from the date of the procedure to 30 calendar days post-operatively. Late events are defined as those occurring from after 30 calendar days post-operatively (from day 31 forward). Events within six months and one year, respectively, are those occurring up to and including 183 days and 365 days following the procedure.

For categorical variables, summary statistics will include counts and proportions. Confidence limits for proportions will generally be given; for binary variables the confidence limits will be computed

¹⁴Little R and Rubin D. *Statistical Analysis with Missing Data*. 2002. John Wiley and Sons, New York.

¹⁵Steele R and Torrie J. *Principles and Procedures of Statistics*. 1960. McGraw-Hill, New York.

using the exact binomial distribution. Supportive multivariate analyses of stratified comparisons of categorical variables will be performed using appropriate logistic or Cox regression.

For continuous variables, summary statistics will include means, standard deviations, medians, and range. Groups will be compared using *t*-tests or analysis of variance, or Kruskal-Wallis tests will be used to compare more than two groups (such as trial sites). When multiple comparisons are performed after ANOVA, Scheffé's method will be used. The exact Wilcoxon test will be used to compare continuous variables where severe departures from normality are observed.

For ordinal variables, comparisons will be performed using the exact Wilcoxon rank-sum test. Unless otherwise specified, the exact form of each algorithm will be the default of SAS[®] Version 9.1 or later. Some preliminary descriptive analyses may be done with other software tools to be specified.

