10.5 POOLING

Data pooling incorporates two factors: combination of data across trial sites and the actual method of obtaining an estimate of the endpoint from combined data. Data will be combined from multiple trial sites for the trial analyses. The justification for this pooling is made on a clinical basis with three critical factors: The basis for pooling comes from: 1) The trial sites must implement one common protocol; 2) The sponsor must provide very close monitoring of study site compliance; and, 3) the trial sites must use common data collection procedures.¹⁶

In order to determine if there is a similar response across the sites to allow the responses to be pooled in the trial the primary safety and effectiveness proportions will be tested for homogeneity by logistic regression using a univariate model of study site within the test group. If the P-value for study site is less than 0.15, differences in study site proportions in response will be assumed to exist and the overall estimate of the proportion in the test patients will be obtained by taking a weighted average of the proportions at each site with the weight being the inverse of the variance of the proportion at that

¹⁶Meinert C. Clinical Trials: Design, Conduct, and Analysis. 1986; Oxford University Press. New York, NY

site.¹⁷ The sum of these weighted proportions divided by the sum of the weights will be the overall estimate for the study. For the safety variable, the differences of the weighted proportions will form the basis of the statistical test and for the effectiveness variable, the overall weighted proportions will be the basis of the test. The test of significance in these circumstances are fully described below.

If the heterogeneity P-value is greater than 0.15, an analysis of the primary effectiveness endpoint by the Fleiss (1993) method will be done.

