If there is heterogeneity among the study sites the test will be additionally adjusted for site differences by the method of Fleiss (1993). If the data from the study sites cannot be pooled to form a common estimate of the treatment effect, the following analysis from Fleiss (1993) will be done. Within each stratum i and treatment group j , the mean proportions across study sites is given by the following formula:

$$\bar{p}_{ij} = \frac{\sum_k W_{ijk} p_{ijk}}{\sum_k W_{ijk}}$$

Where p_{ijk} is the estimated MAE proportion from stratum i and site k for treatment j , and $W_{ijk} = 1/((1/n_{ijk})p_{ijk}(1-p_{ijk}))$. for $i=1-5$, $j = T$ for test and C for Control and k is the site number. The

²¹Mehrotra D. and Railkar R. Minimum risk weights for comparing treatments in stratified binomial trials. *Statistics in Medicine* 2000;19:811-25

differences of the weighted proportions will be computed within each propensity stratum and the test will be done using the method of Mehrota and Railkar using the minimum risk weighting factor. The formula for z is the same as above except that the within stratum estimates of the difference are the given by the following,

$$\delta_k = \bar{p}_{tk} - \bar{p}_{ck}$$

Where \bar{p}_{ik} is given by the formula above. The variance within the stratum of the difference is given by the following.

$$V_i = \left(\sum_{k=1}^{m_t} W_{itk} \right)^{-1} + \left(\sum_{k=1}^{m_c} W_{ick} \right)^{-1}$$

Where m_t is the number of sites in the treated sample and m_c is the number of sites in the control sample.

If the P-value from either test above is less than a one-sided 0.025, then the null hypothesis for this analysis will be rejected in favor of the alternative indicating that the new patients have a statistically significantly smaller rate of MAE than the historical surgical control group.

A descriptive analysis and a Kaplan-Meier analysis of the MAE composite at 30 days will be presented. The descriptive analysis will present the rates for the composite MAE and each individual adverse event that is part of the composite with corresponding 95% exact confidence intervals.

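### When site success rates differ, the primary effectiveness rule rejects H0 for small z and weights sites by the variance, so it passes devices below the 80% goal

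*Combined protocol and SAP*

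**What the plan says.** Sections 10.7.1 and 10.7.3 set H0: P_t ≤ 0.80 against H1: P_t > 0.80 at one-sided 0.05. The default is the exact binomial test. The synopsis names no other test for this endpoint, and section 10.7.2 bases the sample size on it (82 evaluable, 97 recruited).

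Section 10.5 adds a check on sites. The rates are "tested for homogeneity by logistic regression using a univariate model of study site within the test group". If that P-value is below 0.15, a weighted average over sites is used, "with the weight being the inverse of the variance of the proportion at that" site, and "for the effectiveness variable, the overall weighted proportions will be the basis of the test". The section then continues: "If the heterogeneity P-value is greater than 0.15, an analysis of the primary effectiveness endpoint by the" Fleiss method is to be done. Section 10.7.3 has a different trigger: "If the study site success proportions across study site are not homogeneous, then the method of" Fleiss applies.

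On that path section 10.7.3 prints:

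- z = (p̄ − 0.80)/SE, with p̄ = ΣW_k p_k / ΣW_k
- W_k = (1/n_k) p_k (1 − p_k)
- SE = (ΣW_k)^(−1/2)
- the rule "If the $z < 1.645$ ($P=0.05$, one-sided), then the null hypothesis will be rejected in favor of the alternative", after which the endpoint counts as achieved.

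Section 10.6.4 prints the same weight for the safety test against the 56% performance goal. For the stratified safety test, however, it prints the inverse, 1/[(1/n)p(1 − p)]. Section 10.3 says that, unless specified otherwise, "the exact form of each algorithm will be the default of SAS".

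**The concern.** The statistic is positive when the weighted success rate is above 0.80, so evidence for H1 is a large z. The printed rule rejects for every z below 1.645, including all negative values. It is in running text, and nothing elsewhere in the plan corrects it.

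Four further faults affect the same path:

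- **Weight.** p_k(1 − p_k)/n_k is the variance of a site proportion. SE = (ΣW)^(−1/2) is a standard error only if W is the inverse variance.
- **Trigger.** Section 10.5 leads to the Fleiss method both below and above 0.15; section 10.7.3 uses it only when sites differ.
- **Sites at 0% or 100%.** The inverse weight is undefined there, and no handling is given.
- **Site test.** Likelihood-ratio, score (Pearson) and Wald P-values differ greatly with small sites, and none is named.

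Once the path is entered, the weighted z decides the primary effectiveness endpoint. If the error is noticed only after the data are seen, a primary decision rule must be changed post hoc.

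**Working it through.** **The plan's own figure.** Exact binomial, n = 82, p0 = 0.80, p1 = 0.90 (section 10.7.2). The smallest r with P(X ≥ r | 0.80) < 0.05 is 72. P(X ≥ 72 | 0.80) = 0.0458 and power is 0.8057 (stated 80.58%). 82/0.85 = 96.5, so 97. With all 97 analysed the rule is 85/97, with exact alpha 0.0346 and power 0.830. The default test reproduces and points the right way.

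**Direction.** Treat the sites as one pooled proportion, z = (p̂ − 0.80)/√[p̂(1 − p̂)/n], and enumerate the binomial. P(z < 1.645) is:

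| True rate | n = 82 | n = 97 |
|---|---|---|
| 70% | 99.96% | 99.99% |
| 80% | 91.6% | 93.8% |
| 90% | 11.5% | 10.3% |

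The printed rule passes poor devices and usually fails the planned 90% device.

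**Printed weight.** z = ΣW_k(p_k − 0.80)/√ΣW_k. By Cauchy–Schwarz, z ≤ √ΣW_k(p_k − 0.80)² over sites with p_k > 0.80. The maximum of (p − 0.80)√[p(1 − p)] is 0.0333. One-patient sites have weight 0, so with up to 25 sites Σ1/n_k ≤ 25/2. Hence z ≤ 0.0333 × √12.5 = 0.118. Every computable result is below 1.645 and passes. If only the inequality were corrected, none could pass.

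**Example** (assumed sites of 16, 16, 16, 17, 17):

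| Successes | Weight | p̄ | SE | z |
|---|---|---|---|---|
| 15, 15, 15, 15, 13 (73/82) | inverse | 0.914 | 0.0305 | 3.74 |
| 15, 15, 15, 15, 13 (73/82) | printed | 0.859 | 6.01 | 0.010 |
| 12, 11, 10, 9, 7 (49/82) | inverse | 0.608 | 0.0522 | −3.67 |
| 12, 11, 10, 9, 7 (49/82) | printed | 0.594 | 3.82 | −0.054 |

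With the inverse weight, the printed rule fails 73/82 and passes 49/82. The printed weight gives standard errors above 1, impossible for a proportion. These data show the arithmetic only: their Pearson statistics, 3.85 and 4.90 on 4 df (P = 0.43 and 0.30), would not open the path.

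**Simulation.** 600,000 trials per cell, 97 patients; 6, 10 or 20 near-equal sites, or 12 unequal (19, 15, 12, 10, 8, 7, 6, 5, 5, 4, 3, 3). The path opens at P < 0.15; otherwise the exact rule 85/97 decides. With the inverse weight, 0%/100% sites are either dropped or avoided by using (x_k + 0.5)/(n_k + 1) as p_k at every site (0.5 added). Other forms of that correction shift the figures. In the Wald test, 0%/100% sites contribute nothing and df = sites − 1. Ranges over the four layouts, % of trials:

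| Quantity | LR | Pearson | Wald |
|---|---|---|---|
| Path reached, common rate 70% | 17.5–34.2 | 13.5–15.3 | 0.0–9.0 |
| Path reached, common rate 80% | 20.1–31.5 | 13.4–14.9 | 0.0–4.6 |
| Path reached, site rates vary (mean 70%, SD 10 points) | 50.6–57.1 | 31.8–47.4 | 0.0–33.3 |
| Overall success at 80%: printed sign, printed weight | 22.8–34.5 | 16.3–17.9 | 3.4–8.0 |
| Printed sign, inverse weight, sites dropped | 17.9–34.5 | 13.5–17.3 | 3.4–6.2 |
| Printed sign, inverse weight, 0.5 added | 10.7–32.9 | 10.2–15.2 | 3.4–7.4 |
| Both corrected, sites dropped | 2.6–7.6 | 3.0–7.3 | 3.4–5.3 |
| Both corrected, 0.5 added | 4.5–15.2 | 4.1–10.4 | 3.4–4.0 |

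The exact test alone gives 3.5% at 80%.

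On the path, with the inverse weight and printed sign, 98.5–100% (dropped) or 92.9–100% (0.5 added) pass at a true 70%. At a true 90% (LR or Pearson), 23.5–100% pass if sites are dropped and 0.4–23.1% if 0.5 is added. A 0% or 100% site then occurs in 70% of trials with 6 sites and 99–100% with 10 or more.

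**Safety fallback.** The same bound with 0.56 gives |z| ≤ 0.1466 × √12.5 = 0.518, against the 1.96 needed. As printed, no device could meet that goal.

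**The case against.** The sign is an evident slip: the same sentence says one-sided 0.05, H1 is stated twice, and the exact test just above points the right way. The intended weight can be recovered from section 10.5 and from the stratified safety formula in section 10.6.4, and an outer fraction may have been lost in PDF reading. For P above 0.15, section 10.5 asks only for an analysis by Fleiss, not the primary test. With a Wald test and 10 or more sites, overall success at 80% is 3.4–3.7%, essentially the exact test's 3.5%. The exact test itself gives 5.1–9.8% false success if site rates are drawn at random around 80% with SD 10 points.

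Much of this is fair as to intent, and the weight should be checked against the source file. It does not make the printed rule usable. The sign does not depend on PDF reading, and the plan does not say that Wald applies. Restoring both intended formulas still leaves the level unsecured, because 0%/100% sites are not handled. The last point concerns a different target. Section 10.7.3 defines P_t as the proportion among treated patients; for fixed site rates averaging 80% over those patients, the exact test stays at or below its nominal level. If inference to a wider population of sites is wanted, the point stands.

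**Conclusion.** The concern holds and must be fixed before the analysis. On the site-heterogeneity path, the primary effectiveness rule has the wrong direction and prints a weight that contradicts sections 10.5 and 10.6.4. Read literally, it declares success for any computable result. Read with the inverse weight, it still passes nearly every trial on the path at a true 70%. Overall false success at 80% is 10–35% with likelihood-ratio or Pearson and 3.4–8.0% with Wald.

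These figures rest on the assumed site layouts (the plan gives only a maximum of 25 sites and a 20% cap per site), a common true rate and entry at P < 0.15. The ten hot-deck imputations of section 10.2 are not modelled. The direction error and the bounds on z do not depend on the simulation. The default exact test and the sample size are unaffected. The safety consequence arises only if the propensity comparison is abandoned and the sites also differ.

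**What to change.** Preferably, let the exact binomial test decide effectiveness in all cases, as the synopsis states and as the sample size assumes, and report the site-weighted estimate as a sensitivity analysis. This is SAP wording only.

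If the weighted test is kept as decisive, make these changes together:

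1. Section 10.7.3: reject H0 if z > 1.645.
2. Sections 10.7.3 and 10.6.4: print W_k = n_k/[p_k(1 − p_k)], after checking the source file.
3. Section 10.5: exact test when the site P-value is at least 0.15, Fleiss method only below 0.15, and name the site test.
4. Pre-specify the handling of 0%/100% sites, with a simulation showing that one-sided 0.05 is held. Neither handling tried here held it in every layout under all three site tests. Combining small sites as in section 10.4 is not enough: with the sites of 4, 3 and 3 combined, a 0%/100% site remains in 99.5% of trials at a true 90%.

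This costs wording plus a short simulation. Under either option, correct or move the printed sign and weight in section 10.7.3, and correct the weight in the section 10.6.4 safety fallback. Sample size and data collection do not change.

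Two separate clerical points: the exact-test label in section 10.7.3 should read P(X ≥ x_t) to match its sum, and the backward-elimination sentence closing section 10.6.4 should say greater than 0.05.
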